3. ABBREVIATIONS

List all abbreviations / acronyms in alphabetical order, for example:

AF	Atrial Fibrillation
ANOVA	Analysis of Variance
BMI	Body Mass Index
BNP	B-type natriuretic peptide
BSE	British Society of Echocardiography
ECG	12 lead Electrocardiogram
E/e'	Echocardiographic measure of ventricular filling pressures
EF	Ejection Fraction
GCP	Good Clinical Practise
H2FPEF	New diagnostic criteria for HFpEF (Heavy, ≥ 2 Hypertensive medications, atrial fibrillation, pulmonary hypertension, elderly, elevated filling pressure
HFmrEF	Heart Failure with Mid-Range Ejection Fraction
HFpEF	Heart Failure with Preserved Ejection Fraction
HFrEF	Heart Failure with Reduced Ejection Fraction
LV	Left Ventricle
NHS	National Health Service
NIHR	National Institute for Health Research
NT-proBNP	N-Terminal pro-B-type Natriuretic Peptide
PASP	Pulmonary Artery Systolic Pressure
PPI	Patient Public Involvement
QAH	Queen Alexandra Hospital
STP	Scientist Training Programme

4. LAY SUMMARY

Heart failure with preserved ejection fraction (HFpEF) is a complex condition with various causes that is not yet fully understood. Heart failure is a long-term condition where the heart is unable to pump enough blood to meet the demands of the body. Heart failure is then categorised based on ejection fraction, which is the percentage of how much blood the heart pumps out each beat. HFpEF is a form of heart failure where the heart still pumps >50% of its volume each heart beat. Most significantly there is no method of diagnosing or treating the condition. A recent project proposed non-invasive criteria using routinely collected data to predict the likelihood of HFpEF. This was termed H2FPEF and uses: weight, number of hypertensive medications prescribed, age, presence of atrial fibrillation, ventricular filling pressures and pulmonary hypertension. The main limitation of this study is the use of a single centre population from the Mayo clinic in Rochester, US. Another limitation is that the H2FPEF criterion consists of common conditions which could as a result overestimate HFpEF probability. The aim of the investigators is to test the H2FPEF criteria on previous data already held from heart failure clinic database at Queen Alexandra Hospital (QAH) in Portsmouth. Implications of the project if H2FPEF is proved to be accurate on the population is that it can be used within the Trust and other trusts. This would allow HFpEF to be identified quicker at a reduced cost for the trust and reduced risk for the patient avoiding invasive investigations. On the other hand if H2FPEF is found not to be applicable to the population then further research would be required to find the ideal tool or method to identify HFpEF. A follow-up of patients is also proposed to monitor any long-term outcomes and how they respond to treatments.

5. BACKGROUND AND RATIONALE

Epidemiology:

In the UK heart failure is the biggest cause of hospital admissions in people aged over 65, and is associated with poor morbidity and mortality outcomes if not managed effectively (National Institute for Health Care and Excellence [NICE], 2015). Heart failure is a complex heterogeneous condition characterised by typical symptoms and signs indicative of structural or functional cardiac abnormalities which despite normal filling pressures results in failure to deliver oxygen at a rate proportionate to the demands of metabolizing tissues (Ponikowski et al., 2016). Typical symptoms of heart failure include shortness of breath, reduced exercise tolerance, fatigue, orthopnoea and paroxysmal nocturnal dyspnoea; with signs such as peripheral oedema, functional mitral regurgitation, murmur and elevated jugular venous pressure (Allen et al., 2015). All of these signs and symptoms are however not specific to heart failure and could be caused by alternative conditions which makes diagnosis difficult (Oren and Goldberg, 2017).

Heart failure is categorised based on ejection fraction (EF);

- EF <40% - Heart failure with reduced ejection fraction (HFrEF)
- EF 40-49% - Heart failure with mid-range ejection fraction (HFmrEF)
- EF ≥50% - Heart failure with preserved ejection fraction (HFpEF)

The aetiology of HFpEF is less well understood compared to HFrEF because it is not a uniform disease and patients usually have a combination of morbidities, but there is now a greater focus on it as it is just as prevalent (Lam et al., 2011; Dunlay et al., 2017; van Empel and Rocca, 2018). No effective therapies have as yet been found for management of HFpEF, with therapies that have proven effective in reducing mortality and morbidity in HFrEF patients not having the same effect for HFpEF patients, making this an important research focus (O’Gallagher and Shah, 2018). Approximately half of heart failure patients are now believed to have HFpEF, with the prevalence increasing and set to become the dominant form of heart failure as the condition becomes better understood and diagnosed (Banerjee, 2016; Deaton et al., 2018).

Background:

HFpEF was previously characterised as ‘diastolic dysfunction’ but this terminology was changed as it was found that diastolic dysfunction was also seen in patients with ‘systolic dysfunction’ (Borlaug and Paulus, 2011). Myocardial stiffness which leads to increased filling pressures is a common pathophysiologic attribute of HFpEF despite its multifactorial aetiology (Telles and Marwick, 2018). Other common conditions associated with HFpEF include: atrial fibrillation (AF), chronotropic incompetence, pulmonary hypertension, right ventricular dysfunction and endothelial dysfunction; with common non-specific risk factors such as: age, gender, hypertension, obesity, diabetes, metabolic syndrome and renal failure (Borlaug, 2014; Ferrari et al., 2015; Harper et al., 2018). This complex heterogeneity of HFpEF which is not yet fully understood highlights the difficulty that clinicians have in being able to diagnose the condition.

Diagnosis of HFpEF is difficult and as of yet there is no test to confirm diagnosis, with current guidelines saying initial diagnosis should include the presence of typical signs and symptoms, an elevated B-type natriuretic peptide (BNP) (>35 pg/mL and/or N-Terminal pro-

B-type Natriuretic Peptide [NT-proBNP] >125 pg/mL) and ejection fraction $\geq 50\%$ (Lekavich et al., 2015; Ponikowski et al., 2016). Echocardiography is the preferred method of assessing for HFpEF due to it being widely available, non-invasive, and able to provide immediate results (Ponikowski et al., 2016). Recent studies comparing the use of echocardiography against 'gold standard' invasive cardiac catheterisation to assess cardiac filling pressures found echocardiography to be just as accurate and reliable (Anderson et al., 2017; Lancellotti et al., 2017). Implications of this research would be that patients could be assessed as outpatients by focus echocardiography rather than invasively in the cardiac catheterisation lab, which would improve patient experience, enhance patient outcomes and prove cost-effective for trusts.

In response Reddy et al (2018) recently proposed non-invasive diagnostic criteria called H2FPEF which assesses patients based on body mass index (BMI), the number of hypertensive medications they take, presence of AF, pulmonary pressure, age and filling pressure. The advantage of the H2FPEF score is that it uses only non-invasive echocardiography data alongside routine clinical data making it easy to derive. However one key limitation of their study is the population they used was all from the Mayo clinic and so the generalisability of their results has not been tested for other populations, such as those of lower socioeconomic status like in Portsmouth. A further limitation is the parameters chosen to create H2FPEF are all relatively common morbidities and usually co-exist, making it likely that it will over diagnose HFpEF.

Research questions:

The main research question the investigators are investigating is whether the H2FPEF criteria proposed by Reddy et al. (2018) is an accurate predictor of HFpEF on the patient population at QAH. In the original paper by Reddy et al. (2018) they created and tested H2FPEF criteria on their study population from the Mayo clinic, Rochester, US. This population is predominantly Caucasian and of a high socioeconomic status and so lacks generalisability. In response the investigators are testing the H2FPEF criteria on the population at QAH which is of a lower socioeconomic status, to investigate if it remains an accurate predictor of HFpEF.

Risks:

As the investigators study is a retrospective observational study there are no risks to participants, and all data obtained will be anonymised with no personally identifiable data being analysed.

Impact:

The main outcome of this project will be whether the H2FPEF score is able to accurately predict HFpEF on the patient population of QAH, Portsmouth or if it overestimates diagnosis. If the investigator's research hypothesis is accepted then future research will be required to either optimise H2FPEF score or to develop new HFpEF diagnostic criteria. The enigma of HFpEF would continue to be the focus of research with the aim of developing an applicable clinical diagnostic tool. Alternatively if the investigators accept the null hypothesis then the H2FPEF score will have been validated on the population and would have the potential to be used by QAH and other trusts. Future research would then be required on other populations to further assess the generalisability of H2FPEF. The implications of this would be that patients are able to be diagnosed with HFpEF quicker and non-invasively requiring just an ECG, a focus echocardiogram and a routine clinical examination. Consequently invasive

cardiac catheterisation would not be required for diagnosis which would improve patient outcomes and patient service experience, as well as being cost-effective for the trust.

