2. SYNOPSIS

Study Title	A retrospective observational analysis of a cohort with Heart Failure with Preserved Ejection Fraction from a BNP pathway clinic
Problem statement	Heart failure with preserved ejection fraction (HFpEF) is a complex condition with various causes that is not yet fully understood. Most significantly there is no single method of diagnosing or treating the condition. Recently a novel non-invasive diagnostic criterion to predict the likelihood of HFpEF was proposed by Reddy et al. (2018) called H2FPEF. The main limitation of this study was the use of a single centre population from the Mayo clinic in Rochester, US. Another limitation is that the H2FPEF diagnostic criterion consists of common and often co-existing conditions which could as a result overestimate HFpEF probability. The aim of the investigators is to retrospectively test the H2FPEF criteria on the population at Queen Alexandra Hospital (QAH) in Portsmouth, which is of a lower socio-economic status and greater ethnic diversity. Implications of the project if H2FPEF is proved to be generalizable to the population is that it can be used within the Trust and rolled out to others. This would allow diagnosis to be made quicker and more cost effectively using echocardiography and without the need for invasive cardiac catheterisation. On the other hand if H2FPEF is found not to be applicable to the population then further research would be required to find the ideal diagnostic tool.
Research question / hypothesis	The investigator's hypothesis is that when H2FPEF criteria is compared against retrospectively held data for the patient population at QAH that this will overestimate the probability of HFpEF
Study Design	The study is a single-centre retrospective observational analysis
Study Participants	Patients who attended heart failure clinics at Queen Alexandra Hospital between January 1st 2016 – December 31st 2016
Planned Sample Size	2000
Follow-up duration	1 year
Planned Study Period	04/10/2019 – 30/04/2020
Primary Objective	The primary objective of the investigator's project is to test if the H2FPEF score accurately predicts HFpEF on the population at Queen Alexandra Hospital.

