8.2 Primary and Secondary Outcome Measures

Primary outcome measure

- Accuracy of H2FPEF at predicting HFpEF on the patient population will be assessed as specificity and sensitivity as calculated by logistic regression

Secondary outcome measure

- Investigate if H2FPEF overestimates HFpEF diagnosis on the patient population when compared against known BNP levels.
- To evaluate if H2FPEF can be validated on the patient population and be utilised to improve patient pathway for HFpEF.
- To assess patient outcomes after one year, including any changes in medication or treatment as well as number of hospital admissions and reported symptoms.

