13.2 Analysis of Outcome Measures

To determine if the H2FPEF score was accurate in predicting HFpEF the calculated H2FPEF score will be compared against BNP blood test results using the cut-off points stated by the European Society of Cardiology (Ponikowski et al., 2016). To test our hypothesis an analysis of variance test (ANOVA) will be performed to provide one simultaneous evaluation of the data to determine if there is a significant difference between H2FPEF score and diagnosis of HFpEF. A logistic regression analysis will then be carried out to give an odds ratio and provide a predictive analysis of the data. All statistical analysis will be performed using SPSS software.

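### Section 5 allows only two conclusions, overestimation or validation, and neither uses sensitivity and specificity, so a score that misses many HFpEF patients is mislabelled however the null is read

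*Combined protocol and SAP*

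**What the plan says.** The hypothesis in the Synopsis runs in one direction: applied to the hospital's patients, the score "this will overestimate the probability of HFpEF". The Impact text in section 5 presents the main result as a choice between two outcomes, namely "whether the H2FPEF score is able to accurately predict HFpEF on the patient population of QAH, Portsmouth or if it overestimates diagnosis". Each has a consequence:

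- Hypothesis accepted: "If the investigator's research hypothesis is accepted then future research will be required to either optimise H2FPEF score or to develop new HFpEF diagnostic criteria".
- Null accepted: "if the investigators accept the null hypothesis then the H2FPEF score will have been validated on the population", and the score "would have the potential to be used by QAH and other trusts".

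The primary outcome is stated separately. Under section 8.2, accuracy "will be assessed as specificity and sensitivity as calculated by logistic regression". No minimum value is given for either measure, and no score value is named as a positive result. Section 13.2 tests the hypothesis by ANOVA, to "determine if there is a significant difference between H2FPEF score and diagnosis of HFpEF". It does not state the null, the significance level or the sidedness.

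The Synopsis and the lay summary (section 4) also mention a score that turns out not to be applicable, which would call for further research. Neither says what result would show this.

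**The concern.** A diagnostic score can fail by labelling too many patients or by missing patients who have the condition. The plan gives a conclusion only to the first failure. The complement of overestimation contains both accurate scores and scores that under-diagnose, and section 5 calls that whole complement validated. A larger sample or a better test of overestimation would not help, because the gap lies in how results map to conclusions.

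This matters because section 5 expects a validated score to remove the need for invasive confirmation. For that use, missed cases are a central risk. If the meaning of validation is not settled before extraction, it can be settled after the results are known.

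**Working it through.** The plan states no figure to reproduce for this point. The check follows one under-diagnosing score through the stated rule.

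**Inputs.** N = 2000 (Synopsis). Prevalence p, sensitivity Se and specificity Sp are assumptions. Section 5 puts HFpEF at about half of heart failure patients, so p = 0.5 is the centre; 0.3 to 0.85 is covered because prevalence in this clinic cohort is not given.

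**Formulas.**
- Missed cases FN = N·p·(1−Se)
- False positives FP = N·(1−p)·(1−Sp)
- Labelled/true ratio = [Se·p + (1−Sp)(1−p)]/p

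**Two under-diagnosing scores.**

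| | p 0.5, Se 0.45, Sp 0.95 | p 0.7, Se 0.60, Sp 0.90 |
|---|---|---|
| FN | 2000×0.5×0.55 = 550 of 1000 | 2000×0.7×0.40 = 560 of 1400 |
| FP | 2000×0.5×0.05 = 50 | 2000×0.3×0.10 = 60 |
| Ratio | (0.225+0.025)/0.5 = 0.50 | (0.42+0.03)/0.7 = 0.64 |

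**Reading A: the null is that the score does not overestimate.** A directional paired comparison uses z = (FP−FN)/√(FP+FN).
- First score: (50−550)/√600 = −20.4.
- Second score: (60−560)/√620 = −20.1.

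Neither can be declared to overestimate. The null is kept, and section 5 says validated.

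**Reading B: the null is the non-directional one of section 13.2.** The wording allows two versions.
- Labelled against diagnosed numbers: the McNemar chi-square is 500²/600 = 417 and 500²/620 = 403. Both reject.
- Score by diagnosis group, simplified to positive or negative. First score: 45% against 5% positive, pooled 0.25, z = 0.40/√(0.25×0.75×(1/1000+1/1000)) = 20.7. Second score: 60% against 10%, pooled 900/2000 = 0.45, z = 0.50/√(0.45×0.55×(1/1400+1/600)) = 20.6. Both reject.

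The only conclusion section 5 provides when the null is rejected is overestimation, although each score labels fewer patients than have the condition. In the second version, keeping the null would mean that the score does not separate patients with and without HFpEF, yet section 5 would call it validated.

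**Could the study see the failure?** The 95% half-width for sensitivity is 1.96·√(Se(1−Se)/(N·p)). For the first score it is 1.96·√(0.45×0.55/1000) = 0.031; for the second, 1.96·√(0.60×0.40/1400) = 0.026. The failure would be plain in the primary outcome, but the rule does not use it.

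**Why the labelled/true ratio should not decide.** With Se 0.90 and Sp 0.70 held fixed, the ratio is (0.27+0.21)/0.3 = 1.60 at p = 0.3 and (0.765+0.045)/0.85 = 0.95 at p = 0.85. Prevalence alone moves it across 1.

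**Would a sensitivity minimum work at this size?** Take 0.80 purely as an illustration and require the lower 95% limit to exceed it. With n = N·p, the pass probability is Φ{[Se − 0.80 − 1.96√(0.80×0.20/n)]/√(Se(1−Se)/n)}. At p = 0.3, 0.5 and 0.7 (n = 600, 1000, 1400):
- true Se 0.50: about 0 throughout
- true Se 0.85: 0.89, 0.99, 1.00
- true Se 0.90: about 1.00 throughout

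**The case against.** The strongest reply is that section 5 is background narrative and section 13 contains no adoption rule. Accuracy is the declared aim in the research question, in section 7.1 and in the primary outcome, and the Impact text itself opens by asking about accurate prediction. The Synopsis and lay summary make use depend on the score proving generalisable or accurate, and a score that misses cases could fall under their not-applicable outcome. Sensitivity will be reported, so readers would see a poor value.

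Much of this stands, and it limits the point. A reader might infer that a low-sensitivity score is bound to be declared validated and put into use. The documents do not support that. The null is undefined, and under the non-directional test the score would be sent for revision rather than validated, though for the wrong stated reason. Section 5 speaks only of potential use, with more research in other populations.

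A reader might also infer that under-diagnosis is the likely result here. That is not supported either: no cut-off is stated, clinic prevalence is unknown, and section 5 argues for the opposite direction because the score's components are common and coexist.

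The reply does not remove the gap. The not-applicable outcome has no criterion, and nothing in the aims or section 13 overrides the sentence equating an accepted null with validation.

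**Conclusion.** The point holds as a should-fix. The stated conclusions have no place for under-diagnosis and are not tied to the primary outcome. A score that misses many HFpEF patients is called validated under a directional null and overestimating under a non-directional one; neither describes it.

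In the illustrations, 550 of 1000 or 560 of 1400 HFpEF patients are missed, with labelled/true ratios of 0.50 and 0.64. These sizes rest on assumed prevalence, sensitivity and specificity. The logical gap does not: it follows from the wording of the Synopsis, section 5 and section 13.2. The point concerns the conclusion the study would draw. Missed cases would not be hidden, and adoption would not follow automatically.

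**What to change.** State one rule in section 13.2 and bring the Synopsis and section 5 into line with it.

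1. Delete the statement that accepting the null validates the score, and make the hypothesis two-sided, so that error in either direction counts.
2. Before extraction, fix the H2FPEF score that counts as positive, and a minimum sensitivity and a minimum specificity. The investigators should choose and justify these; the 0.80 used above is only an illustration.
3. Conclude from 95% confidence limits:
   - validated, only if the lower limits for both sensitivity and specificity exceed their minimums;
   - under-diagnoses, if the upper limit for sensitivity is below its minimum;
   - over-diagnoses, if the upper limit for specificity is below its minimum (this and the previous conclusion may both apply);
   - inconclusive, otherwise.
4. Report the labelled/true ratio descriptively only, because it depends on prevalence.

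The cost is protocol and SAP wording, with no extra patients. The cut-off and minimums must be chosen and defended in advance, and validation becomes harder to claim.

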6. PRELIMINARY STUDIES

This is the first study undertaken in response to the recent study by Reddy et al. (2018).

7. AIMS AND OBJECTIVES

7.1 Primary Objective

The primary objective of the investigator's project is to test if the H2FPEF score proposed by Reddy et al (2018) accurately predicts HFpEF on the population at QAH, Portsmouth.

7.2 Secondary Objectives

The investigator's secondary objectives are to:

- Investigate if H2FPEF overestimates HFpEF diagnosis on the patient population when compared against known BNP levels.
- To evaluate if H2FPEF can be validated on the patient population and be utilised to improve patient pathway for HFpEF.
- Follow patients up over one year to monitor outcomes

8. STUDY DESIGN

8.1 Summary of Study Design

Data will be collected retrospectively from consecutive patients who meet the inclusion criteria to calculate a H2FPEF score: weight, number of hypertensive medications prescribed, presence of AF or not, presence of pulmonary hypertension or not, age and filling pressure. A total H2FPEF score will then be calculated for each patient as per Reddy et al. (2018) protocol: BMI > 30 kg/m² (2 points), ≥2 anti-hypertensive medications (1 point), paroxysmal or permanent AF (3 points), pulmonary artery systolic pressure >35mmHg (1 point), age >60 years (1 point), E/e' filling pressure > 9 (1 point).

8.2 Primary and Secondary Outcome Measures

Primary outcome measure

- Accuracy of H2FPEF at predicting HFpEF on the patient population will be assessed as specificity and sensitivity as calculated by logistic regression

Secondary outcome measure

- Investigate if H2FPEF overestimates HFpEF diagnosis on the patient population when compared against known BNP levels.
- To evaluate if H2FPEF can be validated on the patient population and be utilised to improve patient pathway for HFpEF.
- To assess patient outcomes after one year, including any changes in medication or treatment as well as number of hospital admissions and reported symptoms.

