Secondary Objectives	
 • Investigate if H2FPEF overestimates HFpEF diagnosis on the patient population when compared against known BNP levels. • To evaluate if H2FPEF can be validated on the patient population and be utilised to improve patient pathway for HFpEF. • To monitor patient responses to treatments and care for one year.
Primary Outcome Measure	To assess the predictive accuracy of H2FPEF at predicting HFpEF on the patient population as calculated by logistic regression, with diagnostic accuracy being assessed by sensitivity and specificity calculations.
Secondary Outcome Measures	
 • ANOVA will be performed to provide one simultaneous evaluation of the data to determine if there is a significant difference between

	H2FPEF score and diagnosis of HFpEF. •To assess number of hospital admissions and any changes in treatment/ care after one year for the population.
--	--

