11.4 Study Assessments

All data will be collected retrospectively from the heart failure clinic database at QAH. Data will be collected on: weight, number of hypertensive medications prescribed, presence of AF or not, presence of pulmonary hypertension or not, age and filling pressure. These are the factors that make up Reddy et al. (2018) H2FPEF score. In addition the patient's ejection fraction and BNP will also be recorded as a measure to determine HFpEF diagnosis. All data will be anonymised and recorded on a Microsoft Excel spreadsheet, with a separate document documenting the pseudonymised data. All data will have been routinely collected as part of the heart failure patient pathway:

- Echocardiography - A non-invasive ultrasound test which takes approximately 30 minutes and has no radiation risk. Echocardiogram results will be used to ascertain pulmonary pressure and diastolic filling pressure. This will have been performed routinely as part of the heart failure patient pathway at QAH. All scans will have been performed on GE Healthcare Vivid echocardiography machines by a trained sonographer from the Cardiac Investigations Unit at QAH. A standard operating procedure exists for performing echocardiogram. In accordance with local practice personal protective equipment is worn for this test. ECG electrodes and ultrasound gel can be a potential risk to the patient with regards to dermatological reaction/sensitivity, however both are hypoallergenic substances.
- 12-lead electrocardiogram (ECG) - A non-invasive test of the electrical conduction of the heart assessing heart rate and rhythm. ECG results will be used to determine if the patient is in AF or not. All ECG will have been recorded with the use of the hospitals standard machine (MAC 1200, GE Healthcare). All tests will have been

performed by trained staff within the Cardiac Investigations Unit at QAH. Standard operating procedures are followed to perform ECG. ECG will have been performed routinely as part of the heart failure patient pathway at QAH.

- Weight - Using a standard trust scale (Marsden Weighing Company, UK)
- Age and Number of hypertensive medications taken - Assessed from patient records

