12. DATA HANDLING AND RECORD KEEPING

12.1 Data Collection Forms

All data will be collected and stored electronically using the following format.

Participant ID	BMI (>30Kg/m ²) Yes/No	≥2 anti-hypertensive medications Yes/No	AF Yes/No	PASP >35mmHg Yes/No	Age (>60 years) Yes/No	E/e' (>9) Yes/No	H2FPEF Score	Patient Outcomes

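### The primary outcome is sensitivity and specificity of H2FPEF, but the plan never states which score, or which predicted probability, counts as positive

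*Combined protocol and SAP*

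**What the plan says.** Section 8.2 (primary outcome) says that accuracy "will be assessed as specificity and sensitivity as calculated by logistic regression". The synopsis words it slightly differently: predictive accuracy "as calculated by logistic regression, with diagnostic accuracy being assessed by sensitivity and specificity calculations".

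Section 8.1 lists the six items and their points (2, 1, 3, 1, 1, 1) and says "A total H2FPEF score will then be calculated for each patient". It does not divide the total into positive and negative.

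Section 13.2 is the analysis section. It says that "the calculated H2FPEF score will be compared against BNP blood test results using the cut-off points stated by the European Society of Cardiology". It then gives the hypothesis test: "To test our hypothesis an analysis of variance test (ANOVA) will be performed". Last comes the regression: "A logistic regression analysis will then be carried out to give an odds ratio and provide a predictive analysis of the data". Sensitivity, specificity, a 2x2 table, an ROC curve and a probability threshold do not appear there.

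On the reference diagnosis, section 11.4 says that "ejection fraction and BNP will also be recorded as a measure to determine HFpEF diagnosis". The background (section 5) gives guideline criteria of BNP above 35 pg/mL and/or NT-proBNP above 125 pg/mL together with an ejection fraction of at least 50%.

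**The concern.** A score with ten possible values has a different sensitivity and specificity at each cut-off. Logistic regression does not remove the choice. It returns a probability for each patient, and a rule is still needed to turn that probability into a positive or negative call. The plan states neither a score cut-off nor a probability rule, so two analysts could follow section 8.2 faithfully and report different primary results from the same patients.

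Two consequences follow. First, a cut-off picked after looking at the data would be judged on the data used to pick it, which tends to flatter the score. The records already exist, so little but prior commitment prevents this. Second, the stated aim is to find out whether a published score works in a new population. Sensitivity and specificity read from a model refitted to this clinic's patients depend on the probability rule and on the clinic's case mix. They do not test the published score at a fixed operating point.

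**Working it through.** The plan gives no accuracy figure to reproduce. The check has a documentary part and an illustrative part.

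**1. Search for a threshold.**
- Section 8.1: item thresholds and points only.
- Section 12.1 (data form): six yes/no items, the total score and patient outcomes; no positive/negative field.
- Section 13.2: cut-offs for BNP only.
- Section 8.2 and the synopsis: no cut-off.

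**2. Count the options.** The points sum to 2+1+3+1+1+1 = 9. Listing all 2^6 = 64 item combinations shows that every integer from 0 to 9 can occur. There are therefore nine non-trivial cut-offs (≥1 to ≥9). This step uses only the document.

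**3. Illustrate the spread. All inputs except the points and N = 2000 are assumed.**
- Items are independent given disease status.
- Central frequencies without HFpEF, in the order BMI, medications, AF, PASP, age, E/e': 0.35, 0.50, 0.15, 0.25, 0.65, 0.50.
- With HFpEF, every log-odds is raised by one common shift, chosen to give the AUC. For AUC 0.80 the shift is 1.174. For AF, logit(0.15) = −1.735; adding 1.174 gives −0.561, a frequency of 0.363.
- Sensitivity at cut-off c = P(score ≥ c given HFpEF); specificity = P(score < c given no HFpEF).

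| Cut-off | Sensitivity | Specificity |
|---|---|---|
| ≥3 | 93.0% | 42.5% |
| ≥4 | 80.5% | 63.8% |
| ≥5 | 64.1% | 80.4% |
| ≥6 | 42.8% | 91.3% |

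Moving from ≥4 to ≥5 costs 80.5 − 64.1 = 16.4 points of sensitivity and gains 80.4 − 63.8 = 16.6 points of specificity.

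**4. Compare with sampling error.** With N = 2000 and an assumed 50% prevalence there are 1000 cases and 1000 non-cases. The Wilson half-width is z·√[p(1−p)/n + z²/(4n²)] / (1 + z²/n). For p = 0.805, n = 1000 and z = 1.96 this is 1.96 × √(0.00015698 + 0.00000096) / 1.00384 = 0.0245, an interval of 77.9% to 82.8%. For p = 0.641 the half-width is 0.0297 (61.1% to 67.0%).

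**5. Vary the assumptions.** Nine scenarios combine the central frequencies, a higher set (0.45, 0.60, 0.25, 0.35, 0.75, 0.60) and a lower set (0.25, 0.40, 0.10, 0.15, 0.55, 0.40) with AUC 0.70, 0.80 and 0.90. The step from ≥4 to ≥5 changes sensitivity by about 4 to 19 points and specificity by about 11.5 to 19 points.

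**6. Read the result from a fitted model instead.** Fit logit(p) = a + b × score. The score at which p reaches p0 is (logit(p0) − a)/b. Take the central case, AUC 0.80, and one dataset at an assumed 30% prevalence. Classifying at p0 = 0.5 gives a crossing of 5.46, so ≥6 is positive: 42.8%/91.3%. Classifying at p0 = prevalence gives 4.09, so ≥5 is positive: 64.1%/80.4%. Same patients, same model, different primary result. Under the 0.5 rule the crossing also moves with case mix: 5.46, 4.09 and 2.02 at 30%, 50% and 80% prevalence.

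**7. Ask whether the odds ratio settles it.** Take another assumed set of frequencies: 0.50, 0.70, 0.40, 0.50, 0.90, 0.80 with HFpEF and 0.35, 0.50, 0.15, 0.25, 0.75, 0.50 without. The odds ratio per point stays between 1.72 and 1.78 for prevalence from 20% to 80%, while the 0.5 rule implies ≥7, ≥5 and ≥2 at 20%, 50% and 80%. The one regression output that section 13.2 names does not determine sensitivity or specificity.

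**The case against.** The best defence is the synopsis. It can be read as two separate steps, regression for predictive accuracy and a direct calculation for sensitivity and specificity, with section 8.2 as a compressed paraphrase. On that reading the criticism of a refitted model falls away. The missing cut-off does not, because the synopsis gives none either.

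Section 8.1 also says that the score follows the publication that proposed it, and that publication may define operating points. A reader might infer from this point that no cut-off exists anywhere; the documents cannot show that. But the citation governs how the total is calculated, and the plan adopts only the points.

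The data form keeps each patient's total, so every cut-off can be tabulated later without new data. That is true and makes the repair easy. It does not protect against choosing the headline cut-off after the results are seen.

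The shift with prevalence deserves limited weight. This is one clinic in one calendar year, so it has one prevalence. The shift bears on whether the result carries over to other settings. It does not show that two analysts of this dataset would disagree; that rests on steps 3 and 6 at a fixed prevalence.

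A reader might also infer that the 2x2 table cannot be built. Section 12.1 says "All data will be collected and stored electronically using the following format", and that format has no field for ejection fraction or BNP. Section 13.3 limits collection to data for the score. But section 11.4 says that both will be recorded. The sections disagree with one another; the data are not shown to be unavailable.

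**Conclusion.** The point stands and should be settled before data extraction. The primary outcome is not defined until a positive H2FPEF result is defined, and section 13.2 does not describe how sensitivity and specificity will be obtained.

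The omission and the count of nine possible cut-offs come directly from the document. The percentages do not. They rest on assumed item frequencies, independence of items, AUC and prevalence, and the size changes with them. In the central illustration, one point on the scale moves each measure by 16 to 17 points, against a confidence half-width of 2.5 to 3 points. In the mildest of the nine scenarios, sensitivity moves by only about 4 points, though specificity moves by at least 11.5 in all of them.

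A reader might infer that the conclusion in section 5 about the score being validated turns directly on this gap. It does not: that conclusion is tied to accepting the null hypothesis, and section 13.2 assigns the hypothesis test to the ANOVA. The direct harm is to the primary outcome itself.

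**What to change.** In sections 8.2 and 13.2, and consistently in the synopsis, drop the statement that sensitivity and specificity are calculated by logistic regression. Say instead:

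- Sensitivity and specificity come from 2x2 tables of the unmodified total H2FPEF score (0 to 9) against the reference diagnosis.
- They are computed at cut-off(s) that the team states in the plan and fixes before data extraction, with 95% confidence intervals.
- Sensitivity and specificity at every cut-off from ≥1 to ≥9, and the AUC with its 95% confidence interval, are also reported.
- Logistic regression on the total score is kept for the odds ratio.

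As a consistency edit, state one reference diagnosis and reconcile section 5 (natriuretic peptide with ejection fraction), section 11.4 (ejection fraction and BNP) and section 13.2 (BNP only). Align the section 12.1 form and section 13.3 with section 11.4, so that ejection fraction and BNP are captured.

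The cost is small: wording, one extra table and added fields on the form. No new tests are needed, since the eligibility criteria already require an echocardiogram and a BNP result. The real burden is that the team must agree and justify the cut-off(s) in advance.
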